4. DEMOGRAPHIC AND BASELINE INFORMATION

4.1 Demographics

Demographic characteristics (age, ethnicity, race), anthropometric characteristics (height, weight at baseline, body mass index [BMI] at baseline), and diagnosis of endometriosis (method, duration) will be summarized by treatment group and overall using FAS and PAS, respectively. All demographic information will be captured directly from EDC.

The denominator for percentages will be the number of subjects with non-missing data in FAS/PAS for each treatment group or for all subjects as applicable. The duration of endometriosis (months) will be calculated as follows:

Endometriosis Duration (months) = ((Date of ICF – Date of Diagnosis + 1)/365.25)×12

For subjects who only have a year of the diagnosis date, the date of January 1 will be assumed. For subjects who have both the year and month of the diagnosis date, the first date of diagnosis (01mmmyyyy) will be assumed.

By-subject listings of demographic, anthropometric, and disease details will be provided.

4.2 Medical History

Medical history will be coded using the MedDRA 24.0 or a later version. Medical history data will be summarized on the PAS by MedDRA System Organ Class (SOC) and Preferred Term (PT). The summary will be ordered alphabetically for SOC, and then PT within SOC. Subjects reporting more than one condition/diagnosis will be counted only once in each row (SOC or PT).

All data will be listed by subject including description of the disease/condition, MedDRA SOC and PT, start date, and end date (or ongoing if applicable).

4.3 Menstrual History

Quantitative measurements of historical menstrual cycle and period in days before screening, and menstrual cycle and period in days during study (from informed consent to end of study) will be summarized by treatment group and overall using PAS. Categorical lengths of historical menstrual cycle (<28, ≥28 - ≤ 35, and > 35 days), historical menstrual period (<3, ≥3 - <5, ≥5 - < 7, and ≥ 7 days), menstrual cycle during study (<28, ≥28 - ≤ 35, and > 35 days), and menstrual period during study (<3, ≥3 - <5, ≥5 - < 7, and ≥ 7 days) will also be summarized.

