5.1 Inclusion Criteria

Subjects are eligible to be included in the study only if all of the following criteria apply:

- 1. Pre-menopausal female subjects, between 18 and 49 years of age, inclusive, at the time of signing informed consent.
- 2. Subject must have a clinical diagnosis of endometriosis (laparoscopy or laparotomy) as documented by medical records within 10 years before screening.
- 3. Subject must have a Composite Pelvic Signs and Symptoms Score (CPSSS, refer to Section 8.11 and 10.9) total score of ≥ 6 at screening with a score of at least 2 for DYS and at least 2 for NMPP.
- 4. Subject must have reported at Baseline at least 2 days of "moderate" or "severe" pain for DYS and NMPP, with NRS score of at least 4 (where 0 represents absence of pain and 10 indicates unbearable pain, refer to Section 8.1.3 and 10.6).
- 5. Mammography or contrast-enhanced breast MRI performed within the last 12 months prior to randomization without clinically significant abnormal findings in subjects aged 40 and over only (subject with BI-RADS Classification 1 3 is eligible for randomization).
- 6. Subject must have at least two consecutive regular menstrual cycle (i.e. 21 to 35 days in duration) prior to Day 1.
- 7. Subject agrees to use required (nonhormonal) birth control methods during the entire length of participation in the study (refer to Section 10.4) and agrees to avoid pregnancy from signing the informed consent until 3 months after the last dose.
- 8. Subject must agree to use only those rescue analgesics (i.e. not prophylaxis) permitted by the protocol during the Screening, Treatment and Posttreatment follow-up Periods for her endometriosis-associated pain. (refer to Section 6.5.1).

Version 6.0 33 of 138 April 11, 2024

- 9. In the Investigator's opinion, subject is able to understand the nature of the study and any risk involved in participation in this study and is willing to cooperate and comply with the protocol restrictions and requirements, including transvaginal ultrasound (TVU).
- 10. Subject agrees not to participate in another interventional study while participating in the present study.
- 11. Subject who is willing to limit alcohol consumption during the study to no more than approximately one alcoholic drink or equivalent [beer (354 mL/12 ounces), wine (118 mL/4 ounces), or distilled spirits (29.5 mL/1 ounce)] per day.

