1.1 Study Design

This is a Phase 2, multicenter, double-blind, placebo-controlled, randomized study to assess the safety and efficacy of HMI-115 subcutaneously administered monoclonal antibody versus placebo in pre-menopausal women with moderate to severe endometriosis-associated pain. The planned study regions include China, the United States of America (USA) and European countries.

The study will comprise of three periods:

1. Screening Period of up to 75 days prior to first dose
 - Screening Visit 1
 - Screening Visit 2 (at least 35 days before Visit 3 to ensure at least 5 weeks baseline pain score obtained before randomization)
2. Treatment Period (12 weeks). Subjects will be given subcutaneous (s.c.) injections Q2W (once every 2 weeks).
3. Follow-up Period of 12 weeks.

Figure 1: Study Design of the Study

IMP: investigational medicinal product.

Eligible subjects will be randomized into four arms: placebo, 60 mg, 120 mg, and 240 mg HMI-115 in a 1:1:1:1 ratio with 38 subjects/arm. The randomization will be stratified with two stratification factors 1) region and 2) participation in the intensive Pharmacokinetics(PK) sampling subset.

A subject is considered to have completed the study if she has completed all phases of the study including the last scheduled procedure (follow-up at Week 25 for safety and to cover 5 half-lives) as shown in the Schedule of Activities (SoA) (Section 1.3 of Protocol).

The end of this clinical study is defined as the date of the last visit of the last subject in the study or last scheduled procedure shown in the SoA (Section 1.3 of Protocol) for the last subject in the study globally.

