7.3.6 Change in Menstrual Period Heaviness from Baseline by Visit

Descriptive statistics will be presented for the changes of days of menstrual period and menstrual cycle, and the changes of mean scores of heaviness (bleeding) collected from eCOA at Week 6, Week12 and Week 24 measurements.

Scores of heaviness (bleeding) for each subject will be listed.

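### SAP 4.3 pools pre-dose, treatment and follow-up menstrual cycles in one by-arm table with no 21-day class, so it dilutes an on-treatment change and cannot count irregular on-treatment cycles (low priority)

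*SAP*

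**What the plan says.** SAP 4.3 (Menstrual History, within the demographic and baseline chapter) says that "menstrual cycle and period in days during study (from informed consent to end of study) will be summarized by treatment group", using the primary analysis set. The cycle-length classes are "menstrual cycle during study (<28, ≥28 - ≤ 35, and > 35 days". The section does not say whether the unit is the cycle or the subject's average.

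SAP 1.1 gives the parts of that window: "Screening Period of up to 75 days prior to first dose", with the second screening visit "at least 35 days before Visit 3 to ensure at least 5 weeks baseline pain score obtained before randomization"; then "Treatment Period (12 weeks"; then "Follow-up Period of 12 weeks".

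Protocol 5.1, criterion 6, sets the study's own definition of regularity: "Subject must have at least two consecutive regular menstrual cycle (i.e. 21 to 35 days in duration) prior to Day 1".

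SAP 7.3.6, under a secondary endpoint, adds a separate analysis: "Descriptive statistics will be presented for the changes of days of menstrual period and menstrual cycle", at the Week 6, Week 12 and Week 24 measurements. SAP 2.1 defines the default statistics for continuous data as n, mean, SD, quartiles, median, minimum and maximum.

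Protocol Table 2-1 lists menstrual change with oligo- or amenorrhea among the conditions that raised prolactin might induce, and calls them very unlikely. Protocol 10.3.1 makes it an adverse event of special interest (AESI), defined as 56 days without bleeding or spotting.

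**The concern.** A table by treatment arm will be read as information about treatment. This one mixes cycles completed before any dose, cycles during dosing and cycles after it, so an effect limited to the dosing period is averaged with cycles that cannot show it, or show it only in part.

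The classes add a second problem. The protocol treats 21 to 35 days as regular. The table's upper limit matches that definition, but there is no lower limit. A regular 26-day cycle and an irregular 19-day cycle fall in the same row.

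At stake is a simple count: how many on-treatment cycles fell outside the regular range in each arm. The AESI does not supply it. It cannot be triggered by short cycles, nor by cycles of 36-55 days. SAP 7.3.6 does not supply it either, because it has no classes and uses one selected cycle per time point.

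**Working it through.** The documents give no figure for the dilution, so there is none to reproduce.

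**Inputs.** Screening 35 days (minimum diary run-in) to 75 days (maximum), treatment 84 days and follow-up 84 days (SAP 1.1). Last dose Day 71 and last visit Day 169, that is 98 days later (Protocol Table 1-2). Week 25 is chosen to cover 5 half-lives (Protocol 4.4). Off-treatment cycle mean 28 days and SD 3 days are assumptions.

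**1. Share of time on treatment** = 84 / (screening + 84 + 84).
- 75-day screening: 84/243 = 34.6%.
- 35-day screening: 84/203 = 41.4%.

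**2. Whole 28-day cycles.**
- 75-day screening: 3 of 2 + 3 + 3 = 8, or 37.5%.
- 35-day screening: 3 of 1 + 3 + 3 = 7, or 42.9%.

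**3. Number of cycles changes with their length.** Pooled mean = total days / total number of cycles, allowing part cycles.
- Shortening 28 to 24 days: pooled mean 26.5 to 26.2, so 38-45% of the change shows.
- Lengthening 28 to 35 days: pooled mean 30.1 to 30.5, so 30-36% shows. Counting whole cycles only gives 29-33%.

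**4. Simulation, complete cycles only.** The menses containing Day 1 starts 0-4 days earlier (SoA footnote 3). Cycles starting from that menses up to Day 84 take the treatment mean. Ranges run from 75-day to 35-day screening.

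| On-treatment mean | Pooled mean | Share of shift shown | Pooled class | Same class, unaffected arm |
|---|---|---|---|---|
| 35 days | 31.0-31.5 | 43-50% | >35 days: 22-26% (on-treatment cycles alone: 50%) | 1% |
| 22 days | 24.9-24.4 | 52-60% | <28 days: 75-79% | 51% |

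In the 22-day case, 37% of on-treatment cycles are below 21 days, against 1% when unaffected. SAP 4.3 has no row for this.

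If the sequence instead starts on Day -35 or Day -75 and only cycles starting on Days 1-84 change, the results are lower. Lengthening gives a pooled mean of 30.4, so 2.4/7 = 34% of the shift, with 18-19% of cycles >35 days. Shortening shows 43-45% of the shift, with 71-72% of cycles <28 days.

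**5. Follow-up is not drug-free.** If 98 days cover 5 half-lives, the half-life is at most 98/5 = 19.6 days. Two half-lives after Day 71 is about Day 110. Counting exposure to that day gives 110/243 = 45% to 110/203 = 54%.

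**6. SAP 7.3.6.** The Week 6 and Week 12 measurements each use one cycle anchored to a treatment-period visit (SAP 7.2.1), so they are not pooled with screening or the body of follow-up.

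**The case against.** The strongest reply is that the plan already describes on-treatment change in SAP 7.3.6, with SD, quartiles and extremes under SAP 2.1, so opposite shifts in different women would not simply cancel unseen. The 4.3 table is descriptive, sits in the baseline chapter and supports no test. Its placebo column is diluted in the same way, so a difference between arms remains visible. The table shells, which might split the periods, are not public.

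Most of this stands. A reader might infer that the table would look reassuring whatever the drug does, that it cannot separate drug from no drug, or that short cycles are hidden. The documents do not support those readings. In the simulations, lengthening to 35 days still gives 18-26% of cycles >35 days against 1% unaffected, and shortening to 22 days gives 71-79% <28 days against 51%. The minimum and first quartile are also reported. Nor is it right that only a third of a change shows: that is near the low end of the calculations. The risk named in Protocol Table 2-1 is oligo- or amenorrhea, not short cycles, and it has its own AESI with by-treatment tables (SAP 8.1).

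The reply does not supply the missing count. SAP 7.3.6 uses one cycle per time point and does not itself name treatment group. Its usual baseline window runs from menses start to menses start, while its Week 12 window runs from menses end to menses end, so a change in period length can enter the difference. A minimum or quartile does not say how many cycles or women were below 21 days.

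**Conclusion.** The point holds as a low-priority improvement to a descriptive table. SAP 4.3 pools three periods, of which treatment is 35-41% of the time, and about 35-60% of a mean shift would show. That range rests on an assumed 28-day mean and SD of 3 days, an effect confined to cycles starting on treatment, and full follow-up; the crudest count for lengthening goes down to 29%. Subjects with no follow-up data would show more, because treatment is then 84/159 = 53% to 84/119 = 71% of their time.

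The lack of a 21-day limit needs no assumption: the <28 class cannot count cycles that the protocol itself calls irregular. An on-treatment change is not lost, because SAP 7.3.6 describes it at Week 6 and Week 12. The gap is the by-arm count of on-treatment cycles outside 21-35 days, including those of 36-55 days. The primary analysis is unaffected.

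**What to change.** In SAP 4.3, replace the single during-study summary of cycle and period length with three: before treatment, treatment and follow-up.

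- Assign each cycle by its start date relative to the menses at or nearest the first dose, and to EOT.
- State a rule for first doses outside menses. SoA footnote 3 places Day 1 on cycle days 1-5, but SAP 7.2.1 provides for a first dose outside menstruation.
- State a rule for cycles that straddle EOT. One that starts just before EOT runs almost wholly in follow-up.
- Use cycle classes <21, 21-<28, 28-35 and >35 days.
- Say whether counts are of cycles or of women.
- Describe early follow-up as washout, not as drug-free.
- Cross-refer to SAP 7.3.6 for changes from baseline.

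The cost is SAP wording and one table shell. The daily bleeding diary (Protocol 8.1.1 and 8.1.5) already holds the data from Visit 2 onwards.

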5. TREATMENT EXPOSURE

All study drug administration information, including reason not administered, start date and time of administration etc., will be presented in the by-subject data listings based on SAF.

Duration of exposure, total volume administered and compliance (%) will be summarized descriptively in tables for each treatment group using SAF.

Duration of Exposure (days) = Date of Last IMP Administration – Date of First IMP Administration +14.

Compliance to treatment (%) = (Total volume administered(ml)/Total volume prepared(ml))*100 for whole study per subject.

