4.2 Scientific Rationale for Study Design

Evaluation of different doses of HMI-115 together with placebo will allow for further evaluation of efficacy and safety of the drug. A parallel design is preferable due to the long half-life of HMI-115, i.e., 6 doses over 12 weeks will be administered to reach steady state.

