6.2 Preparation, Handling, Storage, and Accountability

The lyophilized Drug Product must be stored at 2-8°C. Requirements for aseptic operation should be followed during IMP preparation. Unless administered immediately, for microbiologic consideration, the reconstituted solution should be stored at 2-8°C or room temperature, and administered within 4 hours.

If the solution has been frozen, it must no longer be used for application and should therefore be discarded.

The Investigator or designee must maintain a log to confirm appropriate temperature conditions have been maintained during transit for all IMPs received and any discrepancies are reported and resolved before use of the IMP.

Only subjects enrolled in the study may receive the IMP and only authorized site staff may supply or administer IMPs. All IMPs must be stored in a secure, environmentally controlled, and monitored (manual or automated) area in accordance with the labeled storage conditions with access limited to the Investigator and authorized site staff.

The Investigator, institution, or the head of the medical institution (where applicable) is responsible for IMP accountability, reconciliation, and record maintenance (e.g., receipt, reconciliation, and final disposition records).

Version 6.0 40 of 138 April 11, 2024

Further guidance and information for the final disposition of unused IMPs are provided in the Study Reference Manual or other specified location.

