7.1 Discontinuation of IMP

It may be necessary for a subject to permanently discontinue (definitive discontinuation) the IMP. If the IMP is definitively discontinued, the subject will remain in the study until Visit 10 to be evaluated for safety and efficacy of the IMP. Please refer to Section 10.4 and 8.4.5 for details on contraceptive guidance and collection of pregnancy information.

The Investigator or Medical Monitor (and, if needed, with DMC review) may temporarily hold or stop the dosing of IMP to a subject at any time during the study. For subjects that discontinue IMP for reasons related to safety, unblinding of the treatment assigned to the subject may be carried out if deemed necessary by the Sponsor to assess any potential safety signal or by the Investigator to provide adequate medical care to the subject. All details of reasons, therapies that may have been subsequently started should be well documented and reviewed.

Examples of conditions or symptoms that may warrant holding or stopping IMP at the Investigator's and/or Medical Monitor's discretion include:

- Occurrence of a severe or serious AE assessed as related to IMP
- Repeating premature ventricular contractions (PVC) confirmed by additional ECG examination at least 30 minutes apart, or QTcF interval >500 ms, or increase in QTcF interval >60 ms compared to baseline in absence of possible causes other than the IMP
- Significant decrease of neutrophils count < 1500 mm³ confirmed by repeat measurement

Version 6.0 45 of 138 April 11, 2024

- Pregnancy
- Intolerance of the IMP authorized under this protocol
- If in the Investigator's opinion, continuation with the administration of the IMP would be detrimental to the subject's well-being

Investigator must notify the Sponsor within one calendar day of being aware of an event that may warrant holding or stopping the IMP. If the IMP is held due to safety concerns, approval by the Medical Monitor is required prior to resumption of IMP. If the subject meets the holding or stopping conditions again after resumption (re-challenge), the IMP will be permanently discontinued.

Unless informed consent is withdrawn, subjects who permanently discontinue IMP during the treatment period should attend all subsequent visits up to Visit 10 and complete all procedures (except IMP administration related) as outlined in the SoA.

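### Treatment compliance is measured against volume prepared, not volume planned, so a subject who missed doses can still score 100%

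*SAP*

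**What the plan says.** SAP section 5 (Treatment Exposure) gives the only formula for compliance with study drug in either document: "Compliance to treatment (%) = (Total volume administered(ml)/Total volume prepared(ml))*100 for whole study per subject". It does not define the prepared volume or say what is entered for a dose that was not given.

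The same section plans two other summaries beside it: "Duration of exposure, total volume administered and compliance (%) will be summarized descriptively in tables for each treatment group using SAF". Duration is defined as "Duration of Exposure (days) = Date of Last IMP Administration – Date of First IMP Administration +14". A by-subject listing is also planned: "All study drug administration information, including reason not administered, start date and time of administration etc".

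The planned regimen can be derived from the protocol. Section 4.2 states that "6 doses over 12 weeks will be administered to reach steady state". Table 6-2 gives a total injected volume of 4 mL per dosing visit in each of the four arms. On handling, Protocol section 6.2 says that, unless given at once, "the reconstituted solution should be stored at 2-8°C or room temperature, and administered within 4 hours".

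Gaps in dosing are foreseen. Under Protocol section 7.1 the investigator or medical monitor "may temporarily hold or stop the dosing of IMP to a subject at any time during the study". Section 2.3.1.1 withholds study drug when signs of COVID-19 appear, and section 7.2 asks for dosing to be restarted where possible, however long the hold lasted.

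**The concern.** A compliance percentage is normally read as the share of the planned treatment that the subject received. This ratio answers a different question: of the volume drawn up, how much was injected? Site staff reconstitute and give the drug, so a prepared dose will usually be injected in full and little variation is expected in that quantity. Exposure in this trial is more likely to fall short through doses that were held or missed. If those doses were never prepared, the ratio does not register them.

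What is at stake is the reading of the exposure table. Someone judging whether an arm received adequate treatment would look first at the compliance row, and could be reassured by a figure that does not measure adherence to the six-dose schedule.

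**Working it through.** The documents state no compliance figure or threshold, so there is nothing of the plan's own to reproduce. The check is arithmetic on the SAP formula.

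**Inputs**

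- Planned doses: 6 (Protocol section 4.2; Table 6-1).
- Volume per dose (Protocol Table 6-2): placebo 4 mL; 60 mg arm 1 + 3 = 4 mL; 120 mg arm 2 + 2 = 4 mL; 240 mg arm 4 mL.
- Planned volume: 6 x 4 mL = 24 mL in every arm.
- Dosing days: 1, 15, 29, 43, 57, 71 (Protocol Table 1-1).

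**Step 1. Compliance under two readings of prepared volume**

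Reading (a): a missed dose is not prepared, so it adds 0 mL to both numerator and denominator. Reading (b): a missed dose counts as 4 mL prepared, so it adds 4 mL to the denominator only.

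| Full doses given | Administered (mL) | SAP formula, reading (a) | SAP formula, reading (b) | Administered / 24 mL |
|---|---|---|---|---|
| 1 | 4 | 4/4 = 100% | 4/24 = 16.7% | 16.7% |
| 2 | 8 | 8/8 = 100% | 8/24 = 33.3% | 33.3% |
| 3 | 12 | 12/12 = 100% | 12/24 = 50.0% | 50.0% |
| 4 | 16 | 16/16 = 100% | 16/24 = 66.7% | 66.7% |
| 5 | 20 | 20/20 = 100% | 20/24 = 83.3% | 83.3% |
| 6 | 24 | 24/24 = 100% | 24/24 = 100% | 100% |

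Mixed case: three doses given, one prepared and discarded, two never prepared. The SAP formula gives 12/16 = 75%, against 12/24 = 50% of plan. Partial injection: half of each of six prepared doses gives 12/24 = 50% under either denominator.

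**Step 2. Which reading is more likely**

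The drug is a lyophilisate with a 4-hour limit on use after reconstitution. For a visit that does not take place, or a dose held beforehand, there would normally be nothing to draw up. That points to reading (a), but it is an inference. The eCRF, which would settle it, is not among the documents.

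**Step 3. Whether duration of exposure shows the gap**

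Duration = last dose day − first dose day + 14.

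- All six doses: 71 − 1 + 14 = 84 days.
- Days 1 and 71 only: 71 − 1 + 14 = 84 days, the same, with 8 of 24 mL received.
- Days 1, 15 and 29, then stopped: 29 − 1 + 14 = 42 days.
- Day 1 only: 1 − 1 + 14 = 14 days.

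Duration therefore reflects early stopping but not doses skipped between the first and the last.

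**Step 4. Where the figure is used**

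SAP section 3.3 states no compliance threshold for the per protocol set. The dose-response regressions in section 7.2.5 use assigned dose (0, 60, 120, 240, or its log). The primary analysis in section 7.2.2 does not use compliance either.

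**The case against.** The strongest reply has four parts.

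- **Prepared volume is undefined.** If the eCRF enters 4 mL for every scheduled dose, the formula already equals administered over planned. This stands as a limit on certainty. It is also a reason to write the definition down, because the SAP does not say so.
- **The information is already tabulated.** Total volume administered sits in the same table, and dividing it by a constant 24 mL gives the proposed measure. The listing gives reasons for doses not given, and SAP section 3.1 tabulates discontinuation of study drug. This stands: the shortfall is not hidden. The reader must, however, know that 24 mL is full dosing and disregard a compliance row that may say 100%.
- **The example with doses on Days 1 and 71 only is extreme.** Protocol section 6.1 asks for missed visits to be made up as soon as possible, and early stopping does shorten duration. This also stands; the documents give no expected frequency of mid-course gaps.
- **A fixed 24 mL denominator would score a subject stopped for an adverse event or pregnancy as non-compliant.** This is a fair criticism of an unqualified fix, so the handling of such subjects has to be stated.

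A reader might go further and infer that missed doses can never lower the figure, or that every arm must show close to 100% whatever happens. The documents do not support that: a dose prepared and then withheld, or only partly injected, does lower it. A reader might also infer that the dose-response analysis is distorted. That is not supported either, since the regressions use assigned dose and not compliance.

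**Conclusion.** The point holds as an error in a descriptive summary. On the more natural reading of the SAP formula, compliance does not fall for doses that were never prepared, and any subject given between one and five full doses can score 100% when the share of plan received is 16.7% to 83.3%. Duration of exposure does not correct this for mid-course gaps.

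The conclusion rests on one assumption that the documents make likely but do not state: that no volume is recorded as prepared for a missed dose. If 4 mL is recorded for each, the discrepancy disappears. How far the reported table would be affected depends on how often doses are missed, which the documents do not give.

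The primary result, the secondary results and the dose-response models are untouched. No compliance threshold is stated for any analysis set; the separate protocol deviation specification named in SAP section 3.2 was not available to check.

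**What to change.** In SAP section 5, replace the formula with:

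Compliance (%) = total volume administered (mL) / planned volume (mL) x 100, where planned volume is 4 mL x 6 = 24 mL in every arm. For subjects still on treatment at an interim data cut, planned volume is 4 mL x the number of doses due by the cut.

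Add two items:

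- State whether subjects who permanently discontinue study drug are scored against 24 mL or against the doses due up to discontinuation. Either is defensible, but the choice changes the meaning of the figure.
- Tabulate the number of doses received (1 to 6 in the safety set) by arm.

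If administered over prepared is kept, define the prepared volume for a missed dose and relabel the measure as completeness of injection.

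The cost is a few lines of SAP text, one changed derivation and one added count. Trial conduct, data collection and the efficacy analyses are unaffected.
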